8.0 Criteria for Response

Response criteria -

Ig response – Only IgG levels will be considered for response. IgG levels will be measured as mg/dL by nephelometry (normal range 700-1,600 mg/dL). Response will consist of normalization or improvement by 25% of baseline levels at 6 months during therapy.

Response criteria for the immunization –

Quadrivalent Influenza Vaccine (Fluvarix). HI assay was performed as previously described. Samples were assayed at baseline, 4 weeks (+/- 2 week) and 3 months (+/- 3 weeks) post-vaccination. Response or protection to influenza vaccination was defined as > 40 HU or a fourfold increase in HI titer at 4 weeks (+/- 2 week) and 3 months (+/- 3 weeks) post vaccination, against any of the three strains.

Assessment of the functionality of antigen-specific CD8+ and CD4+ T cells will be performed by intracellular cytokine staining for interferon (INF)-g and tumor necrosis factor (TNF)-a and evaluation of CD154 expression and CD107a cytotoxicity. In brief, PBMCs will be thawed and stimulated for 24 hours with or without the seasonal

influenza vaccine [A/Brisbane/59/2007(H1N1)-, A/Brisbane/10/2007 (H3N2)- and B/Florida/30/2008-like strain; CSL Biotherapies, Hattersheim, Germany]. A response will be considered positive if the % of antigen-specific IFN- γ -, TNF- α -, or CD107a-expressing T cells is ≥ 2 -fold higher than background (unstimulated PBMCs) and if there is a minimum of 0.05% antigen-specific T cells (after subtracting the background or FMO fluorescence minus one).

Pneumococcal Polysaccharide Vaccine - Seroconversion will be defined as at least a two fold increase in levels of antipneumococcal capsular polysaccharide (PCP) IgG antibody or achievement of concentration of $>0.5\mu\text{g/ml}$ in anti-pneumococcal capsular polysaccharide antibody titer (against 6 serotypes). They will be measured before, 4 weeks (+/- 2 week) and 3 months (+/- 3 weeks) post vaccination using ELISA and at the end of the study.

Exploratory Endpoints:

1. Infection rates of influenza or Pneumococcal pneumonia will be recorded during the study.
2. Sustained immunoglobulin responses will be recorded along with serological responses to both the vaccines.
3. Sera will be analysed for cytokine levels and properdin levels.

Correlative studies –

Cytokine levels from stored serum samples (before, 4 weeks (+/- 2 week) and 3 months (+/- 3 weeks) and at the end of the study) – properdin, IFN- γ , IL-10, TNF- α , BAFF, IL-8, CCL3, and CCL4. Influenza specific quantitative (using HLA-A2

restricted FluMP pentamer) and qualitative (using CD107a, IFN-gamma, IL-2 and TNF-alpha by intracellular staining) CD8+ and CD4+ T cell responses will be determined by multiparameter flow cytometry technique from stored PBMC's before, 4 weeks (+/- 2 week) and 3 months (+/- 3 weeks) after influenza vaccination as described [15].

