1.0 Objectives

- To evaluate the ability of lenalidomide to improve the Hypogammaglobulinemia (achieve target IgG response) in patients with CLL.
- To evaluate the ability of lenalidomide to improve the protective antibody titers and serological responses specific to influenza and pneumococcal vaccination (seroconversion response).
- To evaluate the ability of lenalidomide to improve non IgG immune dysfunction such as T cells, cytokines and immunoglobulin subclasses.

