6.0 Evaluation during the Study

Complete blood counts (white blood cell, hemoglobin, platelets and differential), serum chemistry, basic metabolic profile, (sodium, potassium, chloride, CO₂, BUN, creatinine and glucose) will be monitored once every two-four weeks (+/- 4 days) while on lenalidomide.

At 3 months (+/- 3 weeks), patients will have a physical examination, CBC with differential and chemical survey, serum beta-2-microglobulin and IgA, IgG, IgM levels, flow cytometry (CD4+, CD8+). Pregnancy tests for females of childbearing potential and Risks of Fetal Exposure, Pregnancy Testing Guidelines and Acceptable Birth Control Methods, will be discussed with the patients.

Pneumococcal vaccination: Serum levels of antipneumococcal capsular polysaccharide antibodies will be measured before, 4 weeks (+/- 2 week) and 3 months (+/- 3 weeks) after vaccination and at the end of the study (to assess sustainable antibody responses) by ELISA. Influenza vaccination: Haemagglutination inhibition antibody titres (HAI) will be assessed by WHO influenza reagent kit before, 4 weeks (+/- 2 week) and 3 months

(+/- 3 weeks) after vaccination and at end of the study (to assess sustainable antibody responses) [12]. Influenza specific quantitative and qualitative CD8+ and CD4+ T cell responses will be determined by multiparameter flow cytometry techniques from stored PBMC's from the patients before vaccination, 4 weeks (+/- 2 week) and 3 months (+/- 3 weeks) after vaccination [13, 14]. Serum samples for cytokine levels (properdin, IFN- γ , IL-10, TNF- α , BAFF, IL-8, CCL3, and CCL4) will be stored before influenza vaccination at 4 weeks (+/- 2 week), 3 months (+/- 3 weeks) and at the end of the study). PBMC's will be stored at baseline, 4 weeks (+/- 2 week) and 3 months (+/- 3 weeks) after influenza vaccination to determine by multiparameter flow cytometry technique changes in influenza specific quantitative (using HLA-A2 restricted FluMP pentamer) and qualitative (using CD107a, IFN-gamma, IL-2 and TNF-alpha by intracellular staining) CD8+ and CD4+ T cell responses, as described [15].

Criteria for study discontinuation:

Treatment with study drug is discontinued and the patient will be removed from study when any of the following occurs:

1. Lack of response
2. Adverse event(s) that in the judgment of the investigator or the patient may cause severe or permanent harm or which rule out continuation of the study drug
3. Withdrawal of consent
4. Lost to follow-up

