Lenalidomide-related toxicity (defined as any grade 3 or greater non-hematological toxicity) will be monitored using the method of Thall, Simon and Estey [16] and the study will be terminated early if toxicity occurs in more than 40% of patients. Specifically, denoting the probability of toxicity by p , the study will be stopped early if $\text{Prob}(p > 0.40 \text{ data}) > .95$. The above decision criterion will be applied in cohort size of 5. Assuming a beta (.4, .6) priori for p , the above decision criterion implies that we will stop the trial according to the table below. For example, the trial will be terminated if 4 or more patients experienced toxicities among the first 5 patients.

Number of patients	Number of patients with toxicities is at least
5	4
10	7
15	10
20	12
25	15
30	17

The operating characteristics of this study design based on 10,000 simulations are illustrated in Table 2.

Table 2. Operating Characteristics for Toxicity Monitoring Rule.

True toxicity rate	Prob (stop early)	Sample Size 25 th , 50 th and 75 th percentiles
0.20	0.006	35, 35, 35
0.30	0.039	35, 35, 35
0.40	0.152	35, 35, 35
0.50	0.447	10, 35, 35
0.60	0.808	5, 15, 30

For the primary analysis, we will estimate the rate of IgG response along with the 95% confidence interval. As secondary analyses, we will also estimate the rates of Pneumococcus and Influenza seroconversion response, as defined in the response criteria section, and the corresponding 95% confidence intervals. The study will be considered positive in regard to the secondary endpoints if seroconversion is observed in 60% or more of the subjects for at least one of the vaccinations given. Similar method will be used to estimate the rate of influenza or Pneumococcal pneumonia. The duration of IgG response will be estimated using the Kaplan-Meier method. The cytokine levels and serum properdin levels will be summarized using descriptive statistics and will be compared between IgG responders and non-responders using two-sample t-test or Wilcoxon rank-sum test, as appropriate.

Amendments, Deviations, Regulatory

Protocol Amendments

Any amendment to this protocol must be agreed to by the Principal Investigator and reviewed by Celgene. Amendments should only be submitted to IRB after consideration of Celgene review. Written verification of IRB approval will be obtained before any amendment is implemented.

Protocol Deviations

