Lenalidomide-related toxicity (defined as any grade 3 or greater non-hematological toxicity) will be monitored using the method of Thall, Simon and Estey [16] and the study will be terminated early if toxicity occurs in more than 40% of patients. Specifically, denoting the probability of toxicity by p , the study will be stopped early if $\text{Prob}(p > 0.40 \text{ data}) > .95$. The above decision criterion will be applied in cohort size of 5. Assuming a beta (.4, .6) priori for p , the above decision criterion implies that we will stop the trial according to the table below. For example, the trial will be terminated if 4 or more patients experienced toxicities among the first 5 patients.

Number of patients	Number of patients with toxicities is at least
5	4
10	7
15	10
20	12
25	15
30	17

The operating characteristics of this study design based on 10,000 simulations are illustrated in Table 2.

Table 2. Operating Characteristics for Toxicity Monitoring Rule.

True toxicity rate	Prob (stop early)	Sample Size 25 th , 50 th and 75 th percentiles
0.20	0.006	35, 35, 35
0.30	0.039	35, 35, 35
0.40	0.152	35, 35, 35
0.50	0.447	10, 35, 35
0.60	0.808	5, 15, 30

For the primary analysis, we will estimate the rate of IgG response along with the 95% confidence interval. As secondary analyses, we will also estimate the rates of Pneumococcus and Influenza seroconversion response, as defined in the response criteria section, and the corresponding 95% confidence intervals. The study will be considered positive in regard to the secondary endpoints if seroconversion is observed in 60% or more of the subjects for at least one of the vaccinations given. Similar method will be used to estimate the rate of influenza or Pneumococcal pneumonia. The duration of IgG response will be estimated using the Kaplan-Meier method. The cytokine levels and serum properdin levels will be summarized using descriptive statistics and will be compared between IgG responders and non-responders using two-sample t-test or Wilcoxon rank-sum test, as appropriate.

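### Influenza seroconversion counts patients already above 40 HU before vaccination, so the 60% success rule can be met partly or wholly by pre-existing titres

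*Protocol*

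**What the plan says.** Protocol Section 8.0 gives the influenza criterion: "Response or protection to influenza vaccination was defined as > 40 HU or a fourfold increase in HI titer". It is assessed at 4 weeks and 3 months and has to be met "post vaccination, against any of the three strains". The two branches are joined by an or. The baseline sample enters only through the fourfold branch.

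For pneumococcus, the same section says: "Seroconversion will be defined as at least a two fold increase in levels of antipneumococcal capsular polysaccharide (PCP) IgG antibody or achievement of concentration", the concentration being more than 0.5 µg/ml.

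Section 9.0 of the Protocol, repeated in the SAP, takes these definitions over under one name: "we will also estimate the rates of Pneumococcus and Influenza seroconversion response, as defined in the response criteria section". It then sets the success rule: "The study will be considered positive in regard to the secondary endpoints if seroconversion is observed in 60% or more of the subjects", where one of the two vaccines is enough.

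The corresponding objective in Section 1.0 is to "improve the protective antibody titers and serological responses specific to influenza and pneumococcal vaccination (seroconversion response"). Section 6.0 confirms that a pre-vaccination HI sample is taken.

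**The concern.** Seroconversion is a change from before to after vaccination. The influenza definition accepts a level instead, whatever the level was beforehand. A patient above 40 HU to one strain before the dose, with the same titre at 4 weeks and 3 months, is a responder under this text. Requiring both post-vaccination visits to qualify does not remove a titre that persists.

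Nothing elsewhere in the plan corrects this. Section 4.0 has no HI criterion and does not exclude patients for earlier influenza vaccination. Section 3.0 has the vaccine given yearly, so titres from an earlier season may be present before a later dose. Section 9.0 has no exclusion, stratification or adjustment for the pre-vaccination titre.

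The 60% rule is the only success criterion stated for the vaccine objective, and influenza alone can satisfy it. The trial has no control arm, so the pre-vaccination value is its only internal reference for vaccine response, and the absolute-level branch ignores that value. A positive result could not be read as evidence that patients responded to vaccination.

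The pneumococcal text is less clear-cut. Its wording about achieving a concentration may mean reaching it from below, but it does not say so.

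**Working it through.** **The plan's own figure.** The 60% threshold is given without a null rate, target rate, error rate or derivation, so there is nothing to reproduce. The check works out what the definition allows.

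**Inputs from the documents**
- Criterion: above 40 HU or a fourfold rise, any one of three strains (Section 8.0).
- Success: at least 60%, for at least one vaccine (Section 9.0).
- Evaluable number: 31 from the IgG design (Section 9.0). The influenza-evaluable number is not stated, so 20 is shown as an alternative.

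**Assumed inputs**
- b: share of patients above 40 HU to at least one strain before vaccination and still above afterwards.
- q: share above 40 HU for a single strain before vaccination.
- f: true response rate among the remaining patients.

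**Responders needed.** 0.6 × 31 = 18.6, so 19. 0.6 × 20 = 12.

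**Step 1: no vaccine response at all (f = 0).** P(rule met) = P(Bin(n, b) ≥ k).

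| b | n = 31, k = 19 | n = 20, k = 12 |
|---|---|---|
| 30% | 0.0003 | 0.005 |
| 40% | 0.013 | 0.057 |
| 50% | 0.14 | 0.25 |
| 60% | 0.52 | 0.60 |
| 70% | 0.89 | 0.89 |

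If the level branch also required a titre at or below 40 HU beforehand, every entry would be 0, because nobody in this scenario changes.

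**Step 2: effect of the any-strain rule.** If strains are fully correlated, b = q. If they are independent, b = 1 − (1 − q)³. For q = 20%, b = 1 − 0.8³ = 0.488. Under independence b reaches 60% at q = 1 − 0.4^(1/3) = 0.263, so about 26% per strain is enough.

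**Step 3: prior titres plus some true response.** Apparent rate = b + (1 − b) × f, here with f = 25% and n = 31.

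| q | Apparent rate, correlated to independent | P(rule met), correlated to independent |
|---|---|---|
| 0% | 0.250 | 0.00002 |
| 10% | 0.325 to 0.453 | 0.001 to 0.054 |
| 20% | 0.400 to 0.616 | 0.013 to 0.59 |
| 30% | 0.475 to 0.743 | 0.087 to 0.96 |

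**Step 4: true response needed for an expected 60%.** f = (0.6 − b)/(1 − b). This is 60% at b = 0, 33% at b = 40% and 20% at b = 50%.

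**The case against.** **The size is assumed.** No section gives a baseline HI prevalence. Entry requires IgG below 500 mg/dl, and Section 2.0 describes poor antibody responses to immunisation, so prior titres may be low. Meeting the rule wholly through prior titres is plausible only when about half or more of the patients start above 40 HU. This stands, and it limits what can be said about size. It does not show that prior titres are low.

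**Prior titres may not persist.** If both visits must qualify and, as an assumption, 80% of prior titres stay above 40 HU, a prior share of 60% acts as 0.8 × 0.6 = 48%, and the Step 1 probability falls from 0.52 to 0.10. From 50% it acts as 40%, and the probability falls from 0.14 to 0.013. This stands too. The table is in terms of titres that persist, and the text does not say whether both visits are needed.

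**The mixed model is illustrative.** The 25% response rate has no influenza source in the documents. The model also leaves out genuine crossings of 40 HU that are less than fourfold, and its upper values need fully independent strains. The contrast with 0.00002 is therefore somewhat overstated.

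**Protection is a stated aim.** Objective 2 names protective titres, and Section 8.0 itself speaks of response or protection. A level above 40 HU is a legitimate measure of protection. The fault lies in pooling it with response under the name seroconversion and one 60% rule, with no comparison to the level before vaccination.

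**The consequence is limited.** The rule is secondary and drives no stopping decision. Rates come with 95% confidence intervals, and the collected titres would allow protection before and after to be separated at reporting. True, but the plan does not ask for that separation, and the positive declaration would still rest on the pooled rate.

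**Conclusion.** The concern holds. Followed exactly, the plan counts an unchanged influenza titre above 40 HU as seroconversion and lets that count towards a positive secondary result. This follows from the text and needs no assumption.

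How much it matters depends on the unreported share of patients already above 40 HU to at least one strain. With no vaccine response and 31 patients, the effect is negligible at 30% or less and small at 40%. It becomes material from about 50% (0.14), and at 60% the rule is about as likely to be met as not (0.52). With some true response in the remaining patients, lower prior shares also matter. The high probabilities describe what is possible; they are not forecasts.

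The pneumococcal criterion is ambiguous on the same point, no more than that. The primary IgG endpoint and its two-stage rule are untouched. Even a corrected rate would show vaccine response while on lenalidomide, not an effect of lenalidomide, because there is no comparison arm. The change should be made, but the trial's main conclusion does not depend on it.

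**What to change.** In Section 8.0, define influenza seroconversion as, for at least one strain, either a fourfold HI rise from the sample drawn before that vaccination, or a titre at or below 40 HU before and above 40 HU after. Define pneumococcal seroconversion in parallel: a twofold IgG rise, or a concentration at or below 0.5 µg/ml before and above it after.

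In Section 9.0 and the SAP, state that the 60% rule uses these definitions. Report seroprotection, the percentage above each threshold, separately before and after vaccination. That serves the protective-titre part of objective 2.

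A crossing from 40 to 80 HU would still count although it is only twofold. The sponsor may prefer the fold rise alone. Which yearly influenza dose counts, and how many of the six pneumococcal serotypes must qualify, are separate points that should be stated at the same time.

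The cost is wording. No samples or visits are added, because pre-vaccination titres are already measured for both vaccines. The reported seroconversion rate will be lower if some patients start above a threshold, since they can then count only through the fold rise. The change should be made before vaccine-response results are analysed, so that it cannot appear data-driven.

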9.0 Statistical design with exploratory endpoints –

The primary efficacy endpoint is IgG response, defined as having improvement in IgG level by at least 25% at 6 months, compared to baseline. We are targeting an IgG response rate of 50% and we would not be interested in pursuing further if the IgG response rate is 20% or lower. Using Simon's optimal two-stage design, we will enroll 12 patients in the first stage and the trial will be stopped if there are 3 or less IgG responders among the first 12 patients. If there are 4 or more responders, we will continue the enrollment until 31 patients are reached. The effect of lenalidomide is demonstrated and worth pursuing further if among the total 31 patients, at least 10 patients achieve IgG response. This design is based on a type I error rate of 0.025 and a 90% power. Under the null hypothesis, the probability of early termination is 79% and the expected sample size is 16 patients. Patient enrollment will be suspended if there are not at least 3 IgG responders in the first 12 patients and not all 12 patients have been evaluated at 6 months. To account for a potential 10% early drop-out rate, we will enroll 35 patients so as to have 31 patients with both baseline and 6-month evaluations on IgG. Potential reasons for early dropouts are patients' choice, inability to return to our center or changes in CLL status that may require a different intervention. Sensitivity

analysis will be performed to assess the impact of early dropouts. For example, we will analyze the data counting early dropouts either as "failures" (the most conservative approach) or as "missing" (thus, excluded from the analysis) and evaluate the response rate in both scenarios. Also, since the treatment requires at least 3 months of therapy before seeing an effect on immunoglobulin levels, we will also perform a secondary analysis by including only those patients who have been treated for at least 3 months, while counting those early dropouts between 3 and 6 months as "failures".

Lenalidomide-related toxicity (defined as any grade 3 or greater non-hematological toxicity) will be monitored using the method of Thall, Simon and Estey [16] and the study will be terminated early if toxicity occurs in more than 40% of patients. Specifically, denoting the probability of toxicity by p , the study will be stopped early if $\text{Prob}(p > 0.40 \text{ data}) > .95$. The above decision criterion will be applied in cohort size of 5. Assuming a beta (.4, .6) priori for p , the above decision criterion implies that we will stop the trial according to the table below. For example, the trial will be terminated if 4 or more patients experienced toxicities among the first 5 patients.

Number of patients	Number of patients with toxicities is at least
5	4
10	7
15	10
20	12
25	15
30	17

The operating characteristics of this study design based on 10,000 simulations are illustrated in Table 2.

Table 2. Operating Characteristics for Toxicity Monitoring Rule.

True toxicity rate	Prob (stop early)	Sample Size 25 th , 50 th and 75 th percentiles
0.20	0.006	35, 35, 35
0.30	0.039	35, 35, 35
0.40	0.152	35, 35, 35
0.50	0.447	10, 35, 35
0.60	0.808	5, 15, 30

For the primary analysis, we will estimate the rate of IgG response along with the 95% confidence interval. As secondary analyses, we will also estimate the rates of Pneumococcus and Influenza seroconversion response, as defined in the response criteria section, and the corresponding 95% confidence intervals. The study will be considered positive in regard to the secondary endpoints if seroconversion is observed in 60% or more of the subjects for at least one of the vaccinations given. Similar method will be used to estimate the rate of influenza or Pneumococcal pneumonia. The duration of IgG response will be estimated using the Kaplan-Meier method. The cytokine levels and serum properdin levels will be summarized using descriptive statistics and will be compared between IgG responders and non-responders using two-sample t-test or Wilcoxon rank-sum test, as appropriate.

Amendments, Deviations, Regulatory

Protocol Amendments

Any amendment to this protocol must be agreed to by the Principal Investigator and reviewed by Celgene. Amendments should only be submitted to IRB after consideration of Celgene review. Written verification of IRB approval will be obtained before any amendment is implemented.

Protocol Deviations

When an emergency occurs that requires a deviation from the protocol for a subject, a deviation will be made only for that subject. A decision will be made as soon as possible to determine whether or not the subject (for whom the deviation from protocol was effected) is to continue in the study. The subject's medical records will completely describe the deviation from the protocol and state the reasons for such deviation. In addition, the Investigator will notify the IRB in writing of such deviation from protocol.

Investigator Responsibilities

Investigator responsibilities are set out in the ICH guideline for Good Clinical Practice (GCP) and in the US Code of Federal Regulations.

The Investigator will permit study-related monitoring visits and audits by MDACC, Celgene or its representatives, IRB/EC review, and regulatory inspection(s) (e.g., FDA, EMEA, and TPP), providing direct access to the facilities where the study took place, to source documents, to CRFs, and to all other study documents.

The Investigator, or a designated member of the Investigator's staff, must be available at some time during monitoring visits to review data and resolve any queries and to allow direct access to the subject's records (e.g., medical records, office charts, hospital charts, and study related charts) for source data verification. The data collection must be completed prior to each visit and be made available to MDACC and the Celgene representative so that the accuracy and completeness may be checked.

Institutional Review Board/Ethics Committee Approval

The protocol for this study has been designed in accordance with the general ethical principles outlined in the Declaration of Helsinki. The review of this protocol by the IRB and the performance of all aspects of the study, including the methods used for obtaining informed consent, must also be in accordance with principles enunciated in the declaration, as well as ICH Guidelines, Title 21 of the Code of Federal Regulations (CFR), Part 50 Protection of Human Subjects and Part 56 Institutional Review Boards.

The Investigator will be responsible for preparing documents for submission to the relevant IRB and obtaining written approval for this study. The approval will be obtained prior to the initiation of the study. The approval for both the protocol and informed consent must specify the date of approval, protocol number and version, or amendment number.

Any amendments to the protocol after receipt of IRB approval must be submitted by the Investigator to the IRB for approval. The Investigator is also responsible for notifying the IRB of any serious deviations from the protocol, or anything else that may involve added risk to subjects.

Any advertisements used to recruit subjects for the study must be reviewed and approved by the IRB prior to use.

Informed consent

The Investigator must obtain informed consent of a subject or his/her designee prior to any study related procedures as per GCPs as set forth in the CFR and ICH guidelines.

Documentation that informed consent occurred prior to the subject's entry into the study and the informed consent process should be recorded in the subject's source documents.

Study records requirements

The Investigator must ensure that the records and documents pertaining to the conduct of the study and the distribution of the study drug, that is copies of CRFs and source documents (original documents, data, and records [e.g., hospital records; clinical and office charts; laboratory notes; memoranda; subject's diaries or evaluation checklists; pharmacy dispensing records; recorded data from automated instruments; copies or transcriptions certified after verification as being accurate copies; microfiches; photographic negatives, microfilm, or magnetic media; x-rays; subject files; and records kept at the pharmacy, at the laboratories, and at medico-technical departments involved in the clinical study; documents regarding subject treatment and study drug accountability; original signed informed consents, etc.]) be retained by the Investigator for as long as needed to comply with national and international regulations (generally 2 years after discontinuing clinical development or after the last marketing approval). The Investigator agrees to adhere to the document/records retention procedures by signing the protocol.

Premature Discontinuation of Study

Single Center

The responsible local clinical Investigator as well as Celgene has the right to discontinue this study at any time for reasonable medical or administrative reasons in any single center. Possible reasons for termination of the study could be but are not limited to:

1. Unsatisfactory enrollment with respect to quantity or quality.
2. Inaccurate or incomplete data collection.
3. Falsification of records.
4. Failure to adhere to the study protocol.

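### No visible rule scores immunoglobulin replacement, so a month 6 IgG rise produced by replacement started or increased after baseline counts as a lenalidomide response

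*Protocol*

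**What the plan says.** Protocol section 9.0, repeated in the SAP, defines the endpoint: "The primary efficacy endpoint is IgG response, defined as having improvement in IgG level by at least 25% at 6 months, compared to baseline". Protocol section 8.0 says "Only IgG levels will be considered for response", and then: "Response will consist of normalization or improvement by 25% of baseline levels at 6 months during therapy". Neither definition sets a condition on other sources of IgG.

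Two counts of responders decide the trial. At stage 1, "the trial will be stopped if there are 3 or less IgG responders among the first 12 patients". At the end, the drug is judged worth pursuing if, of 31 patients, "at least 10 patients achieve IgG response".

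Immunoglobulin replacement is named once, in section 2.0, as common in CLL patients with repeated infections. Section 3.0 (Recommended Concomitant Therapy) allows blood products as supportive care. The one intercurrent event with scoring options is early dropout: a sensitivity "analysis will be performed to assess the impact of early dropouts".

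The pneumococcal secondary endpoint is also an IgG measure: "Seroconversion will be defined as at least a two fold increase in levels of antipneumococcal capsular polysaccharide (PCP) IgG antibody".

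**The concern.** Replacement supplies the analyte that the endpoint measures. Entry requires IgG below 500 mg/dL, with or without symptoms, so some patients may be candidates for replacement during the first six months. With no control arm, nothing in the design separates a rise caused by an infusion from one caused by lenalidomide. If infusion dates are recorded, the affected patients can be found, but the plan does not say how they are then scored. In an open single-arm trial, that choice would be made with the responder count already known.

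The margin is thin: 10 of 31 passes and 9 of 31 fails, so the scoring of one patient can settle the result. Response status also feeds the duration-of-response estimate and the comparison of cytokines between responders and non-responders.

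**Working it through.** **1. Where a rule could sit.**
- Section 4.0 (eligibility): steroids, experimental drugs, other anti-cancer treatment and moderate or severe acute illness are addressed. Replacement, or a washout from it, is not.
- Sections 5.0 and 6.0 (evaluations): no recording of infusions is listed.
- Section 6.0 (discontinuation): replacement is not a reason for removal, so a recipient stays on study and is scored.
- Section 9.0 and the SAP: sensitivity analyses cover early dropouts only. A recipient who reaches month 6 is not a dropout.

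**2. Size of rise needed.** Baseline is below 500 mg/dL, so 25% is less than 0.25 × 500 = 125 mg/dL. The normalization route in section 8.0 adds no responders: going from below 500 to at least 700 mg/dL is a rise of more than 40% (700/500 = 1.40).

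**3. The plan's own figures.** Inputs from section 9.0: n1 = 12, continue with 4 or more responders, n = 31, p0 = 0.20, p1 = 0.50.
- Early termination at 0.20: P(Bin(12, 0.20) ≤ 3) = 0.795 (stated 79%).
- Expected sample size: 12 + (1 − 0.795) × 19 = 15.9 (stated 16).
- Enrolment: 31/0.90 = 34.4, so 35 (stated 35).
- Success with cut-off R: Σ over x = 4 to 12 of P(Bin(12, p) = x) × P(Bin(19, p) ≥ R − x). For R = 10 this is 0.051 at p = 0.20 and 0.921 at p = 0.50. For R = 11 it is 0.025 and 0.908.

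The stated type I error of 0.025 belongs to a cut-off of 11, not the written 10. That is a separate matter, so results are shown for both.

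**4. Replacement counted as response (illustration).** Assume k of the 31 patients are certain to show the 25% rise, fall at random into the two stages (hypergeometric), and the others respond at 0.20. For k = 1 and R = 10:
- Affected patient in stage 2 (probability 19/31): Σ over x = 4 to 12 of P(Bin(12, 0.20) = x) × P(Bin(18, 0.20) ≥ 9 − x) = 0.0791.
- Affected patient in stage 1 (probability 12/31): Σ over x = 3 to 11 of P(Bin(11, 0.20) = x) × P(Bin(19, 0.20) ≥ 9 − x) = 0.1026.
- Together: (19/31) × 0.0791 + (12/31) × 0.1026 = 0.088.

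| Affected of 31 | False success, cut-off 10 | False success, cut-off 11 |
|---|---|---|
| 0 | 0.051 | 0.025 |
| 1 | 0.088 | 0.047 |
| 2 | 0.146 | 0.084 |

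**5. Opposite direction.** If k patients cannot show a rise because an infusion raised their baseline, and the others respond at 0.50, power goes from 0.921 to 0.902 (k = 1) or 0.880 (k = 2) at cut-off 10, and from 0.908 to 0.885 or 0.858 at cut-off 11.

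**6. Price of non-responder scoring.** Let a share w start or increase replacement, unrelated to drug response. The response probability becomes p(1 − w) in the formula of step 3.

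| w | Power, cut-off 10 | Power, cut-off 11 | Type I error, cut-off 10 | Type I error, cut-off 11 |
|---|---|---|---|---|
| 0 | 0.921 | 0.908 | 0.051 | 0.025 |
| 2% | 0.909 | 0.893 | 0.045 | 0.022 |
| 5% | 0.888 | 0.867 | 0.037 | 0.018 |
| 10% | 0.844 | 0.812 | 0.027 | 0.012 |

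**The case against.** The evidence of exposure is thin. The background sentence concerns CLL patients with repeated infections, and entry requires no infection history. The supportive-care paragraph names blood products, not immunoglobulin. The case report form and Appendices I and D are not supplied, and inclusion item 13 is empty in the text available. Infusions may therefore already be recorded, and a rule may exist out of sight. All of this stands. It limits the claim to the absence of a visible scoring rule and leaves the frequency open.

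A reader might infer that the trial is biased towards success. The documents do not support that. Stable replacement at both samples may show no rise, and an infusion shortly before baseline works against response. The figures in step 4 assume that every affected patient clears 25%, and the documents give neither an infusion rate nor the size of the rise. A calculation on stage 1 alone, with one or two affected among 12, would look more dramatic. It would assume 8% to 17% affected against 3% to 6% in step 4, and would give the chance of continuing rather than of false success, so it is not used.

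A reader might also infer that the plan already prescribes non-responder scoring, because it calls counting dropouts as failures "the most conservative approach". That phrase describes one of two sensitivity scenarios for dropouts. The main count is planned on 31 patients evaluable at both times, with 35 enrolled to reach that number. It sets no precedent for the primary analysis.

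Finally, non-responder scoring follows exposure, not cause: a true responder given one infusion soon after baseline becomes a failure. That is a real cost, shown in step 6, and a reason to call the rule an estimand choice.

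**Conclusion.** The gap holds. Followed literally, both documents count a month 6 rise of at least 25% as a lenalidomide response even when replacement started or increased after baseline produced it, and they do so at both Simon stages. One or two such patients would roughly double or triple the false-success probability (0.051 to 0.088 or 0.146 at cut-off 10; 0.025 to 0.047 or 0.084 at cut-off 11). This assumes a true 20% rate and that each affected patient clears 25%. How often this would happen is not in the documents, and the net direction is unknown. The point should be corrected, with medium confidence in its practical weight; it does not show that the result would be wrong.

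**What to change.** - **Record** the dates of all immunoglobulin replacement from before baseline to end of study. Stopping at month 6 would be too early, because section 3.0 gives pneumococcal vaccine between months 6 and 21, with titres afterwards and at end of study.
- **Primary scoring.** State in sections 8.0 and 9.0, and in the SAP, that a patient whose replacement is started or increased between the baseline and month 6 IgG samples is not counted as a responder in the primary analysis, at either Simon stage. This is a conservative estimand choice for the sponsor to fix in advance.
- **Sensitivity analyses**, each reported as a response rate with 95% confidence interval: (a) exclude those patients; (b) exclude patients infused within a sponsor-defined window before either the baseline or the month 6 sample, including those on unchanged replacement. Analysis (b) catches intermittent infusions that happen to fall just before one of the samples. If the number analysed differs from 31, the Simon cut-off does not apply to that analysis.
- **Pneumococcal endpoint.** Add a similar sensitivity analysis for IgG titres drawn after an infusion.

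The cost is a few sentences and one concomitant-medication field, plus the power loss in step 6, since true responders who start or increase replacement count as failures. Power falls below the stated 90% once about 3% are affected at cut-off 10, or about 1% at cut-off 11; one patient of 31 is 3.2%. Type I error cannot rise from this scoring, but at cut-off 10 it stays above 0.025 across the range shown, so the cut-off needs its own correction. The change concerns scoring only and restricts no care.
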